#### Participant Information Sheet

A written/electronic version of the PIS will be emailed/given to the participants by the research team, detailing no less than: the exact nature of the trial; the implications and constraints of the protocol and any risks involved with taking part. At this time a screening number will be allocated to the parent/carer (by the research team) which should be used until they have been randomised into the study and a trial ID allocated. Due to time constraints parent/carer will be contacted by telephone/text or email for any subsequent appointments should they wish to participate in the trial.

It will be clearly stated that the participant is free to withdraw from the trial at any time for any reason without prejudice to current or future care, and with no obligation to give the reason for withdrawal. A potential participant may wish to consider the information, and take the time and opportunity to ask questions of the Investigator, their GP or other independent parties to help inform their decision of whether they would like to participate in the trial. The parent/carer will be given time (at least 24 hours to consider the information before being asked to provide consent); where a parent/carer doesn't require any additional time consent can be obtained without delay.

Informed Consent will be obtained before any trial procedures are performed, by the trial site specific researcher at a face to face meeting at the participant's home where possible. Where this isn't possible it will be obtained by remote means on a video call facilitatedby a consent

form posted to parent/carer prior to appointment. . The research team member will check the parent/carers eligibility to participate, provide a detailed unbiased explanation as to what the trial involves (including benefits, risks and details contained in the PIS) and answer any questions they may have.

Informed Consent will then be obtained by means of participant dated signature and dated signature of the person who explained the trial and obtained the Informed Consent. If this process is completed remotely by video call, a consent form will be posted to the parent/carer with the PIS. The researcher taking the consent will request the parent /carer signs the form, which will be witnessed by the researcher. The researcher will also sign a consent form to confirm they have witnessed this. The researcher will then request that participant shows a copy of the completed consent form and a recording/copy will be taken of the document only. A pre-paid envelope will be provided for the participant to return the original signed consent form to the researcher.

The person who obtained the consent will be authorised to do so by the Chief/Principal Investigator as detailed on the Delegation of Authority and Signature log for the trial. For remote informed consent procedure recording /copy of forms will be retained with along with the original signed form which will be retained at each site within the Investigator Site File (ISF). A copy of the signed ICF will be given to participants and a copy sent to their GP informing them of parents/carers participation in the study.

Baseline Assessment will take place at the same time immediately following consent. Data relating to each participant including administration of the questionnaires with the parent/carer will take place. Once the baseline Case Report Forms (CRFs) and questionnaires have been completed the researcher will notify the Leicester Clinical Trials Unit (LCTU) of the new participant. This will be conducted within 3 working days from the researcher receipt of confirmation of verbal consent from the Regular HV of the identification of a parent/carer. At this point a unique personal trial identification number will be assigned.

# 9.3 Randomisation

Randomisation will be managed and carried out by LCTU. To ensure HV team clusters are evenly distributed, they will be randomly allocated either to the control or intervention group on a 1:1 basis, stratified by site.

Allocation of each HV Team cluster will be carried out when the first parent/carer's informed consent is obtained in each HV team.

The regular HV will be not be notified which group their HV team has been allocated at any point during the trial.

The researcher who has performed the consent with the parent/carer and subsequently completes all assessments, will also be blinded to the allocation of each cluster and will not know which allocation an individual participant belongs to.

Any unintended unblinding by the researcher will be recorded and another assessor will complete all further assessments for that participant. At each assessment, the outcomes assessor will be asked to guess the treatment allocation of the participant.

There will be a Research Administrator team member who will remain unblinded to the allocation and will be informed by LCTU of which of the two trial arms each HV team cluster has been allocated to and which HV team cluster subsequent participants belong to. This Research Administrator team member will be responsible for informing all participants after they have attended their baseline assessment, of their arm allocation within the trial. They will also be informed that they should not disclose the results of this allocation to the researcher who is performing the follow-up visits or their regular HV. SC trained HV will be informed if a new participant is enrolled into an intervention cluster and has requested CBT to enable delivery of the intervention. The SC Trained HV whilst not openly unblinded to cluster allocations, will be aware of those participants that require them to conduct intervention delivery.

# 9.4 Trial Allocation

Participants will be notified of which arm they have been allocated to Intervention or Control, by the Research Administrator team member. This will be performed within 1 working day of notification of the allocation of randomisation, with a telephone call, followed up by an email. At this point the participant will be reminded that that they should not disclose what arm of the trial, they have been allocated to, to any other member of the research or HV team.

# Intervention Arm (SC Package) consists of three elements:

- 1. SC Booklet
- 2. SC Website
- 3. Cognitive Behaviour Therapy (CBT) Session's

Participants will be given the choice as to which of the three possible intervention packages they can access; the SC website, a copy of the SC booklet and CBT sessions. They can chose all of these elements or a combination of any of the three. The research administrator will provide the participant with individualised access to SC website, post or email the SC booklet if requested and notify the SC Trained HV if the participants requests CBT sessions.

The SC Trained HV will organise the CBT sessions with the participants where requested. Participants will also have access to usual NHS HV services delivered by their regular HV.

Where randomised to the intervention arm, participants should receive delivery of the first session within 3 working days of the date the SC Trained HV was notified of their request. Continuity between members of the research team and intervention delivery and responding quickly once a participant is enrolled should be ensured. Participants will be contacted by telephone text or email. This is to help retention in the trial and ensure support is received quickly by the participant who has requested this.

Participants will normally be offered between 1 and 4 sessions of one to one support from a SC Trained Health Visitor which would normally be delivered at home but could be delivered remotely if circumstances (such as Covid-19) demand this. Additional sessions up to a maximum of 6 can be provided where the SC CBT trained HV considers these to be needed. All sessions will be delivered on a weekly basis but must not exceed 6 weeks from date of the first CBT session.

Participants sessions will be recorded (if selected) to allow SC Trained Health Visitors to be monitored and assessed to certify their competence in level 2 CBT skills.

SC Trained HV will audio record the sessions with parents, using an access restricted trial mobile phone/laptop, no identifiable information will be recorded.

All SC trained HV's will upload the recording using trial ID numbers only, to the NIHR Hub secure site where restricted access will only be provided to the SC CBT practitioner trainer. Once accreditation has been received no further recordings will be required and all recordings will be destroyed. We will ask participants and SC Trained HVs to consent to the recordings of these sessions.

Participants will also have access to usual NHS HV services delivered by their regular HV throughout the duration of the study.

Website use will be measured by the objective metrics provided by Google Analytics.

SC Trained HV's will record on a paper CRF the type and amount of intervention each participant in the intervention received. This data will be entered into the SC Database. This will help to assess cost of their overall package to be compared to routine services.

#### Control Arm

Participants allocated to the control arm, will continue to receive usual NHS HV services. However they can request on completion of the trial (16 weeks post baseline assessment, the SC booklet and/or access to the SC website.

They will be provided with an individualised access code for the website (identifiable as control participant).

#### 9.5 Follow up

Follow-up assessments will take place at 8 and 16 weeks after baseline assessment, (which should be completed -1/+1week of the due date). The researcher will telephone or text the participant with appointment times. The researcher will go through each of the questionnaires with the participant in order to complete them. This can be undertaken via the telephone/video call or at the participant's home. Parental/Carer Evaluation of how they found the care they received has the potential to unblind the researcher, therefore the researcher will give a questionnaire to the participant to capture their views of the package received, both groups will also be asked about sharing of the SC materials. This will be completed by the participant not in sight of the researcher (blinded to allocation) and returned in a sealed signed envelope to the research administrator (unblinded to allocation). If the follow up appointment is completed over the telephone /video call, this will be emailed to the participant from the research administrator (unblinded) and requested it is emailed directly back to a secure access restricted email address. Data relating to this will be entered by the research administrator into the SC database, managed by the Leicester Clinical Trials Unit.

To support parents/carers and HV involvement and minimise differential recruitment or follow-up, parents/carers in both groups will be advised at the point of consent by the research team, that their GP will be notified of their participation by letter. However, only when the participants has completed their 16 week follow-up assessment and their participation in the trial has concluded, will the GP be informed of which group the participant was allocated to, intervention or control group. Any parents/carers still concerned about their infant's excessive crying at follow-up or those who require further support will be advised to contact their Regular HV or contact their GP. The GP will also be informed of this.

Participants in the **control group** can request a copy of the SC booklet or access to the SC website intervention resources if required on completion of their involvement in the trial.

To recognize their contribution to the research, participants in both the intervention and control groups will be given a £30.00 shopping voucher at their 16 week follow-up and where indicated on the consent form a summary of the trial findings upon completion and publication of the trial.

Contamination between the groups is unlikely, given the precautions taken, as described previously. Accidental prior knowledge of a HV team's trial arm allocation may bias the recruitment selection process whilst participants who are allocated to control may lose interest and withdraw from the trial prematurely. At the 8 and 16 week follow up the researcher will be asked to guess the treatment allocation of the participant. Additionally, HV team's recruitment and retention rates will be monitored and compared across the trial duration.

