# 9 TRIAL PROCEDURES

# 9.1 Cluster Identification

The sites participating in the trial have been chosen to represent diverse urban and rural settings and socio-economic and cultural groups. HV teams within sites vary in size and the communities they serve. Therefore, with their clinical leaders, we will identify the team(s) that will form a cluster within the trial, comprising of HVs working closely together. Consent to randomise a cluster will be sought. These HV team clusters will be randomised between control (usual HV services) and intervention (usual plus SC services) groups.

Randomisation of a HV team cluster will occur when the first participant is consented from that team cluster. Within each site area, we will ensure that socioeconomically diverse and minority, as well as majority, communities, are represented. As well as using the NIHR BAME Toolkit  to involve and recruit minority groups in culturally appropriate ways, we will include a sub-study directly aiming to improve these groups' involvement in the trial. We will also work with our PPI Co-applicant and collaborators to refine our recruitment methods and ensure that they recognise community as well as scientific priorities.

The target recruitment rate (estimated from the feasibility study data) will be on average 0.4 participants per month per cluster, across all clusters. Feasibility data indicated the incidence of excessive crying babies is around 20%; of those asked to participate the consent rate was around 60%. Each site will have varying birth rates, however, and the recruitment rate will be partly determined by the blinded researcher team capacity to contact, consent and assess potential participants in each of the sites and HV team clusters.

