# 9.2 Identification and Recruitment

#### Participant Identification

Parent/Carers will be introduced to the trial with a leaflet that will either be sent to all Parent/Carers with their new birth letter (wherever possible) and /or provided at the first (HV) visit.

If a parent/carer raises a concern of an excessive crying infant with their Regular HV, that HV will seek verbal consent from the parent/carer for their details to be passed onto a member of the research team. Regular HV will notify the trial site specific researcher by site secure email the details of the parent/carer to be contacted.

GP's located within the recruiting site will also be able to refer parents/carers who raise a concern of an excessive crying infant at their GP review/appointment to a member of the study research staff. They will need to obtain verbal consent from the parent/carer, to provide their contact details to the research team. The GP will be asked to complete a GP referral form which will confirm the Health Visitng team that parent/carer is registered with, this will also provide confirmation that verbal consent has been obtained from the parent/carer. This referral form will be sent by secure email to the local Surviving Crying research team.

Parents/carers can also contact their local site research team directly, to find out more about the study. Researchers will ask parents/carers which Health Visiting Team (Cluster) they are assigned. For any potential participant' that the researcher is not informed of the Health Visiting Team (Cluster), they will check on their local system for this information only.

All participants taking part in the study will continue to receive Usual Health Visiting services as normal.

The study will be promoted with Study Promotional Posters, these will be displayed in several different settings such as GP surgeries in community settings where parent/carers might attend, which will also include maternity, ante-natal units and charities. Additionally promotional material will be used for social media for Charities and websites such as 'mumsnet' and 'crysis'.

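### The GP is told a participant's arm at 16 weeks, usually while that participant's HV team is still recruiting, so a GP who also refers parents may foresee the arm of later referrals to the same team

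*Protocol*

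**What the plan says.** - **Unit and time of allocation.** Section 9.1: "These HV team clusters will be randomised between control (usual HV services) and intervention (usual plus SC services) groups". It adds: "Randomisation of a HV team cluster will occur when the first participant is consented from that team cluster". Everyone recruited later from that team enters an arm that is already set.
- **When the GP learns the arm.** Section 9.5 holds the information back "only when the participants has completed their 16 week follow-up assessment and their participation in the trial has concluded"; only then "will the GP be informed of which group the participant was allocated to, intervention or control group". The trigger is the individual's completion. Nothing makes it wait for the team, or the trial, to stop recruiting.
- **GPs as referrers.** Section 9.2, Participant Identification: "GP's located within the recruiting site will also be able to refer parents/carers who raise a concern of an excessive crying infant". It continues: "The GP will be asked to complete a GP referral form which will confirm the Health Visitng team that parent/carer is registered with". The amendment history shows that GP referral was added at version 4.0.
- **Concealment from others.** Section 9.3: "The regular HV will be not be notified which group their HV team has been allocated at any point during the trial". Section 9.4 reminds participants not to reveal their arm to other members of the research or HV team. It does not mention GPs.
- **The hazard.** Section 9.5: "Accidental prior knowledge of a HV team's trial arm allocation may bias the recruitment selection process". The same section says that team recruitment and retention rates will be monitored and compared.

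**The concern.** Most participants in this cluster trial are recruited after their cluster has been allocated. The comparison is then protected from selection only if the people who send parents to the trial do not know which arm a new parent will enter. The protocol keeps the arm from one referrer, the regular HV, but has the trial itself send it to another, the GP. The 16-week rule protects outcome assessment in the participant who has finished. It does not protect parents still to be recruited from the same team. The timing takes no account of the referring role that GPs acquired at version 4.0.

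A GP who knows that a team's parents receive the SC package has a reason to refer more of them, or the more distressed ones, and less reason to refer from a control team. The arms could then differ in number, in severity and in characteristics that no baseline measure captures.

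**Working it through.** **1. The plan's own sample size (section 14.1), to confirm the inputs.**
- Individual randomisation: n per arm = (z₀.₉₇₅ + z₀.₉₀)² × (1/3.78 + 1/3.06) / [ln(10.5/8.5)]² = 139.2, rounded up to 140, so 280 in total, as stated.
- Design effect: 1 + [(0.625² + 1) × 4 − 1] × 0.037 = 1.169, stated as 1.17.
- 280 × 1.17 = 328; 328/4 = 82 teams; 82 + 4 = 86 teams.
- Recruits per team: 4/0.88 = 4.55. Total: 86 × 4/0.88 = 391, against 392 stated.

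The figures reproduce, and this point changes none of them.

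**2. When the first letter can go out.** Set the team's first participant at month 0. Sixteen weeks is 112/30.44 = 3.68 months, or 3.45 to 3.91 months across the one-week window either side.

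**3. How far the team has recruited by then.** The rate is 0.4 per team per month (section 9.1).
- Recruited by the first letter: 1 + 0.4 × 3.68 = 2.47.
- Still to come: 4.55 − 2.47 = 2.08, which is 2.08/4.55 = 46% (44% to 48% across the window).
- Last participant: (4.55 − 1)/0.4 = 8.9 months after the first, so about five months after the first possible letter.
- At the pace implied by the pilot target, 56/(20 × 9) = 0.31 per month: 1 + 0.31 × 3.68 = 2.14 recruited, 2.41 (53%) to come.

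**4. By team size.** Section 14.1 assumes a range of 2 to 12. With later recruits arriving at random (Poisson) at 0.4 per month:

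| Team size | Chance the team is still recruiting at the first letter | Mean number recruited after it |
|---|---|---|
| 2 | 0.23 | 0.23 |
| 3 | 0.57 | 0.80 |
| 4 | 0.82 | 1.61 |
| 5 | 0.94 | 2.55 |
| 8 | about 1.0 | 5.53 |
| 12 | 1.0 | 9.53 |

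The smallest teams have usually finished. Teams of average size or larger usually have not.

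**5. How many participants could be affected.** The documents do not give the two figures needed: the share of participants referred by GPs and the number of practices whose patients fall under one team. The following therefore rests on assumptions.
- Recruited after the first letter, trial-wide: 0.457 × 392 = 179.
- With an assumed GP share of 10% to 30%, and one practice per team: 18 to 54. Given that share, this is an upper bound.
- With participants spread evenly over several practices per team, a referral counts only if the same practice already holds a letter. Simulating teams of four or five at 0.4 per month gives 9 to 28 for three practices, 6 to 18 for five, and 4 to 12 for eight.
- All of these take 392 as the base. Anyone recruited before version 4.0 could not have come by GP referral, so the true base is smaller.

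**The case against.** **The reach is narrow.** A reader might infer that the letter reveals the arm of every later referral from the team. The documents do not support that. The letter goes to one participant's GP. Referrals by HVs, self-referrals and referrals by GPs without a letter are not directly affected. This objection stands, and it limits the point to GPs who have had a letter.

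**The GP must make a link.** Section 9.5 does not say that the letter names the HV team or explains that allocation is by team, and the letter template is not shown. The referral form gives the team of the new parent, not that of an earlier participant who came through an HV. This stands as a condition. Even so, the form makes the team a visible fact, and a GP may well know which team serves the practice.

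**Leakage to the regular HV.** A reader might also infer that the arm reaches the regular HV through the primary-care record, against section 9.3. Nothing in the protocol says that the arm is filed where HVs read it, and a letter to a GP is not a notification to the HV. That reading should not be pressed.

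**Other safeguards.** A GP referral only passes on contact details. A researcher blinded to allocation checks eligibility, takes consent and completes baseline, and the parent learns the arm only afterwards. Section 14.3 adjusts for individual baseline EPDS and its cluster mean, and section 9.5 monitors team recruitment rates. These limit the harm without restoring concealment. Adjustment deals with the measured score only. Monitoring sees a difference in numbers after it has arisen, and would miss a shift in severity at equal numbers.

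**Conclusion.** The point holds in a limited form. By its own rule the trial discloses a team-level allocation to a potential referrer while the team is usually still recruiting. About 46% of an average team's recruitment follows the first possible letter (about 53% at the pilot-target pace). That figure assumes steady recruitment at the planned rate and 4.55 participants per team; for teams of about two the issue seldom arises.

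The number of participants who would actually come through an informed GP, and any resulting bias in the EPDS comparison, cannot be computed from the protocol. The 18 to 54 figure is a ceiling under an assumed 10% to 30% GP share and one practice per team, not an estimate. The affected group may well be a small minority. The case for acting is that the breach is initiated by the trial, falls under a hazard the protocol itself names, cannot be fully repaired in analysis and costs little to close.

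**What to change.** - **Section 9.5.** Keep the 16-week GP letter, reporting that participation has ended and any advice given about further support, but without the arm. Release the arm to the GP only after recruitment to that participant's HV team has closed, or at the end of the trial. Allow earlier release on request for safety or safeguarding.
- **Section 9.4.** Extend the participant's non-disclosure reminder to referring GPs, on the same terms and with the same exception. Without this, a participant may tell the GP before or after week 16, and the change to the letter would close only part of the gap.
- **Consistency.** Check sections 9.2 and 9.3 against the new wording, so that concealment covers both kinds of referrer.

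The cost is a protocol amendment and revised letter and reminder wording. No visits, staff or participants are added, and the sample size is unchanged. The downside is that the GP learns the arm some months later; in an average team, the first participant's GP would wait roughly five months longer.

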# 4.7 Flow Diagram (Clusters)

#### Flow diagram cont/d

#### **5 SCIENTIFIC ABSTRACT**

Around 20% of infants cry for prolonged periods during the first four postnatal months. Where parents cannot cope, this can lead to parental depression, poor parent-child relationships, problems with child development, and infant abuse in rare cases. With National Institute for Health Research Health Technology Assessment (NIHR HTA) support, we have completed a feasibility study to develop the 'Surviving Crying' (SC) package with the aim of supporting parents in this position. 52 parents of excessively crying infants and 50 NHS health visitors (HVs) provided evaluation data. 30 parents met clinical criteria for depression at baseline, halving to 15 after receiving the SC package. Parents' NHS contacts reduced. All 52 parents and 85% of the HVs wanted the package to be included in the NHS. Most (86%) parents were willing to participate in a controlled trial of the package.

**Population:** Parents/carers over 18 years of all backgrounds with a healthy infant up to 20 weeks old who report concern about their infant's excessive crying to their HV.

**Intervention:** Access to the SC support package, SC Booklet, Website, and option of CBT session 1- 6 session delivered to parents by SC Trained HVs, in addition to usual NHS HV services. Comparator: Usual NHS HV services.

**Primary outcome:** Edinburgh Postnatal Depression Scale (EPDS) score measured 8 weeks after baseline.

**Secondary outcomes:** EPDS score at 16 weeks post baseline; proportion of parents with EPDS score of 10 or more, validated measures of parental anxiety, sleep, social supports, parent knowledge of infant crying, amount of infant crying, parents' ratings of how frustrating and problematic the crying is for them, at both 8 & 16-week follow-ups.

**Other measures:** Parental and infant health, breast-feeding persistence; NHS contacts; parents' use and parent and HV ratings of services; at 8 weeks post baseline, health economic measures at both 8 and 16 weeks follow ups.

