#### **8 ELIGIBILITY CRITERIA**

#### 8.1Cluster Identification criteria

Clusters are defined as a 'team' of health visitors who work closely together to cover families in a given geographical area within an NHS or Local Authority Health Visitor services site. All HV teams that offer services to parents that have new babies are eligible to take part in the trial. Commissioners and providers of HV services for a given geographical area will be approached to take part in the trial through Clinical Research Networks, Social Services, Institute of Health Visiting networks and 'snowballing techniques'. Once a site has agreed to take part in the trial it will be asked to identify the HV teams that could potentially take part. Consent to randomise each HV team within a site is assumed to have been given once a site agrees to take part in the trial.

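### The precautions behind the claim that contamination is unlikely do not address parents passing on the booklet or website login, and section 9.5 and the outcome table do not agree on when sharing is asked about

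*Protocol*

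**What the plan says.** Section 9.5 of the protocol gives the assurance: "Contamination between the groups is unlikely, given the precautions taken, as described previously". It does not list the precautions, so they have to be gathered from earlier sections:

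- Section 8.1: "Clusters are defined as a 'team' of health visitors who work closely together to cover families in a given geographical area".
- Section 9.3, on allocation of clusters: "they will be randomly allocated either to the control or intervention group on a 1:1 basis, stratified by site". Both arms can therefore exist within one site.
- Section 9.3, on staff: "The regular HV will be not be notified which group their HV team has been allocated at any point during the trial".
- Section 9.3, on what participants are told: "they should not disclose the results of this allocation to the researcher who is performing the follow-up visits or their regular HV". Section 9.4 repeats the reminder and again directs it at research and HV staff.
- Section 9.4, Intervention Arm: website access is individual, CBT is arranged by the SC-trained HV once notified of a request, and the research administrator will "post or email the SC booklet if requested".
- Section 9.4, Control Arm: the booklet and website can be requested only after the 16-week assessment.

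On measurement, section 9.5 describes a questionnaire on the care received and adds that "both groups will also be asked about sharing of the SC materials". That paragraph opens with follow-up at 8 and 16 weeks and does not tie the questionnaire to one visit. The outcome table (7.3) has a row for parent and HV evaluation of services with a single tick, at 8 weeks. The abstract has "parent and HV ratings of services; at 8 weeks post baseline".

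**The concern.** The assurance rests entirely on precautions described elsewhere, and those precautions leave one route open. The instructions to participants protect blinding: they concern who may learn the arm, not who may receive the materials. The protocol contains no request that intervention parents keep the booklet or login to themselves. An emailed booklet can be forwarded at once, and section 6.2 says the booklet carries the website's information as far as possible, so an individual website login does not contain that content. The website and booklet are also the most widely used parts of the package: in the feasibility study almost all parents used one or the other, against half for CBT.

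If SC material reaches control parents before they are assessed, the difference in EPDS between arms shrinks and power falls. If sharing is not asked about at 16 weeks, a small or null difference at 16 weeks cannot be examined for sharing that took place after week 8.

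**Working it through.** **1. Each precaution against the route in question (parent to parent)**

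| Precaution | Section | Bears on parents passing on materials? |
|---|---|---|
| Clusters are geographical HV teams | 8.1, 9.1 | Limits it: neighbours tend to share a team. Does not prevent it across teams in one site |
| Regular HV and assessor blinded | 9.3 | No: acts on staff |
| Participants asked not to disclose their arm | 9.3, 9.4 | No: concerns disclosure to research and HV staff |
| Individual website access | 9.4 | Limits it: a login can still be passed on |
| CBT only through a notified SC-trained HV | 9.3, 9.4 | Limits it for the CBT sessions; not for the booklet |
| Control access only after 16 weeks | 9.4 | Limits official supply; not informal supply |

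Taken together these give some support to the word unlikely. None of them deals with a forwarded booklet or a shared login.

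**2. When sharing is asked about**

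Section 9.5 covers both visits without restriction. The outcome table ticks the evaluation row at 8 weeks only and has no separate row for sharing. The abstract puts service ratings at 8 weeks but does not mention sharing. The two readings are therefore 8 and 16 weeks (9.5) or 8 weeks only (table).

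**3. The plan's own sample size, reproduced first**

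Inputs from section 14.1: means 10.5 and 8.5; Gamma k of 3.78 and 3.06; two-sided 5%; 90% power; 4 analysed per cluster; coefficient of variation 0.625; ICC 0.037.

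- Per arm: n = (1.960 + 1.282)² × (1/3.78 + 1/3.06) / [ln(10.5/8.5)]² = 10.507 × 0.5913 / 0.04465 = 139.2, so 140 per arm and 280 in total (stated 280).
- Design effect: 1 + [(0.625² + 1) × 4 − 1] × 0.037 = 1.169 (stated 1.17). 280 × 1.17 = 327.6 (stated 328).
- Clusters: 328/4 = 82, plus 4 = 86 (stated 86).
- Recruitment: 4/0.88 = 4.55 per cluster; 86 × 4.55 = 391.3 (stated 392).

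The sample size arithmetic is sound. The 12% inflation is for data loss and non-compliance with the primary outcome; contamination is not named.

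**4. Illustration of dilution**

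Let c be the share of controls who obtain SC materials and f the fraction of the 2-point effect they gain. Both are assumptions; the documents give neither.

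- Control mean: m = 10.5 − 2cf.
- Standard error of the log ratio with 328 analysed: √[0.5913 / (164/1.169)] = 0.065.
- Power = Φ[ln(m/8.5)/0.065 − 1.96].

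| c | f | Difference (points) | Power, 328 analysed | Power, 344 analysed |
|---|---|---|---|---|
| 0 | – | 2.0 | 90.2% | 91.5% |
| 5% | 1 | 1.9 | 87.4% | 88.9% |
| 10% | 0.5 | 1.9 | 87.4% | 88.9% |
| 10% | 1 | 1.8 | 84.1% | 85.8% |

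The last column applies if the 4 spare clusters also contribute (86 × 4 = 344).

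**The case against.** The strongest reply is that section 9.5 says unlikely, not impossible, and that the described precautions justify the word. Much of this stands. Area-based clusters are the main protection, and CBT cannot be forwarded as an attachment.

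Enrolment is also sparse. At 0.4 participants per cluster per month, 43 intervention clusters over 8 sites give 0.4 × 43 / 8, about 2 intervention parents per site per month, or about 4 in any 8-week window. To contaminate an outcome, one of them must reach an enrolled control parent under a different team before that parent's assessment. The 2-point target is also for the whole package including CBT, so a forwarded booklet is unlikely to carry all of it. A reader might infer that contamination is likely or that the trial is underpowered. The documents support neither: they give no contamination rate, and losses beyond those tabulated need rates they do not make plausible.

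A reader might also take it as settled that sharing is asked only at 8 weeks. That is an inference from the evaluation row and the abstract. The abstract is a weak guide to timing, since the same sentence puts breast-feeding persistence at 8 weeks while section 7.2.2 gives 8 and 16. What stands is the mismatch between 9.5 and the table.

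Website use is recorded through Google Analytics (section 9.4), which may help to detect unusual use of the site. It does not detect a forwarded booklet.

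Finally, the information sheet, call script and booklet are not shown and may already carry such a request. If so, the protocol need only say so. As written, section 9.5 relies on precautions described in the protocol, and this one is not among them.

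**Conclusion.** The point holds in a limited form. The precautions reduce contamination, but none addresses parents passing on the booklet or login, so the assurance in 9.5 claims more than the described measures cover. Section 9.5 and the outcome table must be reconciled on when sharing is asked about. If the table governs, the gap is weeks 8 to 16 and touches only the 16-week secondary outcomes. A reader might infer that the primary analysis is left unmonitored; it is not, because both readings include the 8-week item, at the time of the primary EPDS.

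The size is illustrative only. It rests on the plan's Gamma inputs, 328 analysed and assumed contamination: about 3 percentage points of power if 5% of controls gain the full effect or 10% gain half, and about 6 points if 10% gain it in full. The sample size is not in question. This is a cheap improvement worth making, not a defect that threatens the trial.

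**What to change.** - **Section 9.4:** add to the existing allocation call and follow-up email a request that intervention parents do not pass the booklet or website login to anyone outside their household while the trial is recruiting.
- **Sections 7.3 and 9.5:** state that the sharing and exposure item is collected at both 8 and 16 weeks, by the existing sealed-envelope or Research Administrator route, so that assessors stay blinded. Give it its own row in the outcome table.
- **Section 9.5:** replace the cross-reference with a list of the actual precautions, including the new request.

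The cost is one line in a script and one extra item at 16 weeks through a route that already exists. Neither the sample size nor the primary analysis changes. Some parents will share anyway, so the request reduces contamination without removing it, and the 16-week item shows how much was reported.
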